14.0 Risks and Benefits

14.1 Risks of Harm:

Identify all research-related risks of harm to which the subject will be exposed for each research procedure or intervention as a result of participation in this study. Consider the risks of breach of confidentiality, psychological, legal, social, and economic risks as well as physical risks. Do not describe risks from standard care procedures; only describe risks from procedures done for research purposes

The study will not collect any PHI and pose no significant risk to medical professionals who will apply the tourniquet and blinded observers. However, the study participants may experience minor pain or discomfort when a tourniquet is applied. Previous work has demonstrated temporary and minor pain with tourniquet use.³

14.2 Measures to Minimize Risks of Harm (Precautions, safeguards):

For each research procedure or intervention, describe all measures to minimize and/or eliminate risk of harms to subjects and study personnel

Given that medical professionals will be the ones who apply the tourniquet and on site, any discomfort or pain mentioned by study participants will be addressed immediately. Tourniquet application is anticipated to cause temporary pain when tightened (similar to a blood pressure cuff). If a participant expresses a desire to stop, the medical professional will stop immediately and remove the tourniquet, and recommend follow up if the pain does not quickly subside. The tourniquets will be applied for a very brief period of time - likely less than 60 seconds for each application. This brief application is very unlikely to cause vascular, nerve, or other tissue damage. Anyone with symptoms following tourniquet application will be instructed to follow-up with an emergency department or their physician as appropriate.

14.3

Confidentiality Protections (for research records, data and/or specimens):

Describe in detail the plan to maintain confidentiality of the research data, specimens, and records throughout the study and at its conclusion (e.g., destruction, long term storage, or banking). Explain the plan for securing the data (e.g., use of passwords, encryption, secure servers, firewalls, and other appropriate methods). If data will be shared electronically with other team members/collaborators outside the institution, describe the method of transmission and safeguards to maintain confidentiality. Explain whether this study may collect information that State or Federal law requires to be reported to other officials or ethically requires action, e.g., child or spouse abuse

Each participant will be assigned a study ID number and data collected from this research study will be stored on a USU network computer and backed up on Google Drive. Only study personnel will have access to the study information and data /records.

14.4

Potential Benefits:

Describe any real and potential benefits of the research to the subject and any potential benefits to a specific community or society

If the individuals in the research are considered experimental subjects (per 10 USC 980), and they cannot provide their own consent, the protocol must describe the intent to directly benefit all subjects

There is no anticipated direct benefit to participants from participation in the study. However, information collected from this research study would help ongoing efforts of developing a layperson tourniquet.

14.5

Privacy for Subjects:

Describe the measures to protect subject's privacy during recruitment, the consent process, and all research activities, etc.

Participants will be assigned a study ID number upon the completion of informed consents. All study procedures will be conducted in a private room at USU's Multidisciplinary Laboratories.

14.6
Incidental or Unexpected Findings:

Describe the plan to address incidental findings and unexpected findings about individuals from screening to the end of the subject's participation in the research. In cases where the subject could possibly benefit medically or otherwise from the information, state whether or not the results of screening, research participation, research tests, etc., will be shared with subjects or their primary care provider. State whether the researcher is obligated or mandated to report results to appropriate military or civilian authorities and explain the potential impact on the subject

Not Applicable

15.0
Study Monitoring

15.1 Your study requires either Data and Safety Monitoring Plan (DSMP) or a Data and Safety Monitoring Board (DSMB).

- DSMP
- DSMB
- Both
- Not Applicable

A DSMP should describe the plan to monitor the data to verify that the data are collected and analyzed as specified in the protocol. Include who will conduct the monitoring, what will be monitored, and the frequency of monitoring. It should also include the plan to ensure the safety of subjects

Data confidentiality and security will be maintained at all-time regarding participants' information (i.e., consent documents) and all collected information. The PI will review data for timeliness of submission, completeness, and adherence to the study protocol. Data monitoring will start at the time of participant registration and throughout until completion of the study. Study progress, adherence to protocol, and timeline of data entry, will be tracked closely throughout the study. Research personnel will maintain a clear record and documentation of all collected information, and ensure the accuracy of the record and documentation.

16.0
Reportable Events

16.1 Reportable Events: Consult with the research office at your institution to ensure requirements are met. Describe plans for reporting unexpected adverse events and unanticipated problems. Address how unexpected adverse events will be identified, who will report, how often adverse events and unanticipated problems will be reviewed to determine if any changes to the protocol or consent form are needed and the scale that will be used to grade the severity of the adverse event.

Consult with the research office at your institution to ensure requirements are met

- Describe plans for reporting expected adverse events. Identify what the expected adverse events will be for this study, describe the likelihood (frequency, severity, reversibility, short-term management and any long-term implications of each expected event)
- Describe plans for reporting unexpected adverse events and unanticipated problems. Address how unexpected adverse events will be identified, who will report, how often adverse events and unanticipated problems will be reviewed to determine if any changes to the research protocol or consent form are needed and the scale that will be used to grade the severity of the adverse event

Because all study procedures will be conducted in person and medical professionals will apply tourniquets, any adverse events related to this study will be observed and addressed immediately.

Anticipated but not serious adverse events, such as minor discomfort or pain, will be reported on the Progress Report, which is generally performed on a 12-month cycle. More frequent Progress Reports may be required at the discretion of the IRB.

Serious adverse events are unlikely. Tourniquets left in place for prolonged periods of time (typically greater than 2 hours) have an increased risk of serious complications such as limb loss (amputation), compartment syndrome (muscle and nerve damage requiring surgery), and permanent nerve damage (weakness, numbness, pain in leg). We anticipate a very brief tourniquet application (no more than one minute) which will mitigate this risk.

Unanticipated adverse events will be identified by either medical professionals if a participant sees their physician or an emergency department, or research staff on-site if there is an immediate problem. Examples of less serious unanticipated adverse events include severe pain, extensive bruising, or temporary nerve injury (numbness, burning, pins-and-needles sensations).

All serious adverse events that are related to or may be related to study procedures will be reported by the PI within 24 hours by submitting an adverse event report to the IRB and a written follow-up report within 5 business days.

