The procedures will then be repeated to a participant's other leg for the other arm. For example, if a participant is initially assigned to the CAT and uses the right leg for tourniquet application. The participant will then be in the SMART TQ arm for the left leg.

Termination Procedures

For the first tourniquet application on each leg, the observer will use doppler ultrasound to assess the participant's foot for a present or absent dorsalis pedis pulse. The observer will make the assessment at the location previously marked with a surgical marker. As soon as the pulse is determined to be present or absent, the observer will verbally tell the medical professional, "remove the tourniquet now."

For the second tourniquet application on each leg, the medical professional will tighten the tourniquet on top of the neonatal blood pressure cuff as described. The study team member will record the pressure. As soon as the pressure is noted, the study team member will tell the medical professional, "remove the tourniquet now."

Participant Post-study Assessment

Following the application of two tourniquets to both legs, the study team will ask the participant to rest while lying on the table for five minutes. After five minutes, the study team member will ask the participant the following questions:

- Do you have any persistent pain beyond mild aching at the application site?
- Do you have numbness, tingling, or other abnormal sensations?
- Does your leg feel weak?

If the answer is yes to any question, the team member will ask the participant to rest for five more minutes and re-ask the questions. If the answer to any question is still yes, the study team member will recommend that the participant seek medical care at an emergency department or with the participant's physician. If the study team member or participant is concerned that they are experiencing a medical emergency, they will call 9-1-1 and alert any of the medical professionals assisting with the study for assistance.

If the answer to the questions is no, the study team member will ask the participant to walk up and down the hall in the MDL. The study team member will observe the participant ambulating. If the person feels normal while walking, they can be discharged from the study.

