The study team member will be advised to follow-up with their physician or emergency department for medical care if either leg develops worsening pain, swelling, redness, coldness, or bluish or pale color, or if they have shortness of breath or chest pain. The study team member will advise the participant that some mild local bruising or redness in the area of the tourniquet application may occur and that it does not require medical evaluation.

In addition, given the SMART TQ is an abbreviated investigational device, we will follow the abbreviation requirements specified by the FDA. Please see the "Devices" section for detailed information.

Describe all the data variables, information to be collected, the source of the data, and how the data will be operationally measured.

The outcome variables in the study are: 1. the participants' resting blood pressure, 2. the presence or absence of dorsalis pedis pulse after tourniquet application, and 3. the surface pressure reading when the tourniquet is tightened. At the beginning of the study, participants will be asked to complete a demographic information sheet. On this sheet, they will fill out their age, gender, race, and ethnicity. The demographic information sheet is attached to this protocol.

10.3 At any point in the study, will you request, use, or access health information in any form, including verbal, hard copy and electronic?

Yes No

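### The last scheduled safety check is 5 to 10 minutes after the final application, and the protocol text does not say how a later event reaches the PI

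*Combined protocol and SAP*

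**What the plan says.** Section 10.1 (Participant Post-study Assessment) sets the timetable. After both legs are finished, "the study team will ask the participant to rest while lying on the table for five minutes". Three questions follow, on persistent pain, abnormal sensation and weakness. If any answer is yes, "the team member will ask the participant to rest for five more minutes and re-ask the questions"; if a symptom persists, the participant is advised to seek care. If the answers are no, an observed walk follows: "If the person feels normal while walking, they can be discharged from the study".

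The same section then gives advice for after discharge, to "follow-up with their physician or emergency department for medical care if either leg develops worsening pain, swelling, redness, coldness, or bluish or pale color", and adds shortness of breath and chest pain. As printed, the person so advised is the study team member, not the participant.

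Section 16.1 (Reportable Events) states that "any adverse events related to this study will be observed and addressed immediately", because procedures take place in person. For events that were not anticipated it says: "Unanticipated adverse events will be identified by either medical professionals if a participant sees their physician or an emergency department", and continues "or research staff on-site if there is an immediate problem". Its examples of the less serious ones are severe pain, extensive bruising and temporary nerve injury. The PI reports related serious events to the IRB within 24 hours and in writing within 5 business days.

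**The concern.** SMART TQ is an investigational device. The plan expects that some symptoms may appear after the participant has left, yet it schedules nothing that would find them. It relies on the participant seeking care and on someone then telling the study, and neither section 10.1 nor section 16.1 describes the second step. The 24-hour serious-event report cannot start until the PI knows of the event.

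What is at stake is how far a safety statement at the end of the trial can reach. Followed as written, the trial could report no adverse events when the data reliably support that only for the time in the study room.

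**Working it through.** **1. Window.** Section 10.1 gives 5 minutes to the first set of questions, and 5 + 5 = 10 minutes to the second, which is asked only after a yes. The walk and discharge follow. No later call, visit or questionnaire appears in the protocol text. A participant still symptomatic at 10 minutes is advised to seek care, with no scheduled contact to learn the outcome.

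**2. Events the protocol names, against what is asked.**

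| Event | Named in | Covered by the three questions? | Stated route after discharge |
|---|---|---|---|
| Severe or worsening pain | 16.1, 10.1 | Yes, at 5 to 10 minutes | Own physician or emergency department |
| Temporary nerve injury | 16.1 | Yes, at 5 to 10 minutes | Only the general advice in 14.2 to seek care for symptoms |
| Extensive bruising | 16.1 | No | Only the general advice in 14.2; 10.1 says mild bruising needs no evaluation |
| Swelling, redness, coldness, colour change, shortness of breath, chest pain | 10.1 | No | Own physician or emergency department |

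No row has a stated step that brings the finding to the study.

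**3. Who identifies later events.** Section 10.1 defines medical professionals as the staff who apply the tourniquets. In section 16.1 the term could mean those staff or the clinicians whom the participant consults. If the clinicians are meant, they are outside the study and no notification is described. If the staff are meant, how they would learn of the visit is not described. The on-site half of the sentence covers only immediate problems.

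**4. Exposure.** At most 20 participants × 2 legs × 2 applications per leg = 80 tightenings in the study session, 4 per participant. The number for the one training participant is not stated.

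**5. Illustration of incomplete capture.** The documents give neither a delayed-event rate r per participant nor a probability c that such an event reaches the study. Both are assumed here: r from 1% to 10%, c from 10% to 100%. The chance of recording at least one event in 20 participants is 1 − (1 − r·c)^20.

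| r | c = 100% | c = 50% | c = 25% | c = 10% |
|---|---|---|---|---|
| 1% | 18.2% | 9.5% | 4.9% | 2.0% |
| 2% | 33.2% | 18.2% | 9.5% | 3.9% |
| 5% | 64.2% | 39.7% | 22.2% | 9.5% |
| 10% | 87.8% | 64.2% | 39.7% | 18.2% |

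If no event is recorded, the one-sided 95% upper limit on r is (1 − 0.05^(1/20))/c. With full capture this is 1 − 0.05^(1/20) = 13.9%. At c = 50% it is 27.8% and at c = 25% it is 55.6%. At c = 10% the formula exceeds 100%, so nothing is excluded.

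**The case against.** A reader might infer that safety is assessed only in those few minutes, that no route to the study exists, and that delayed harms will be missed. The documents do not support any of the three.

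- Staff are present and observe throughout (sections 14.2 and 16.1), so 5 to 10 minutes is the last scheduled check, not the only one.
- The consent form was not available. Section 13.4 says that it explains the risks, and section 17.1 says that each participant keeps a copy. It may tell participants whom to call.
- Participants have campus access, first contact a research team member themselves, and can reach the PI about withdrawal (sections 12.1, 13.1 and 13.6). They may well report a problem unprompted.

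A reader might also infer that thrombosis is a named event that the plan fails to look for. Section 16.1 does not list it among its example events, and section 12.6 excludes people with a history of deep venous thrombosis, pulmonary embolism or a hypercoagulable condition. Nor do the questions ignore the listed examples: pain and nerve symptoms are asked about, and bruising is the one left out.

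The strongest remaining argument is about size. The objective is non-inferiority in occlusion, safety is not among the outcome variables, applications are expected to last about a minute, and the IRB memoranda class the study as minimal risk. Even complete follow-up with no events would leave an upper limit of 13.9%. This limits the weight of the point but does not remove it: informal channels are not a stated ascertainment method, and sections 10.1 and 16.1 still leave later events without one.

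**Conclusion.** The point holds as a gap in ascertainment and should be corrected. Scheduled safety observation ends 5 to 10 minutes after the final application, identification of later unanticipated events depends on the participant seeking care, and sections 10.1 and 16.1 do not say how such an event reaches the PI. Delayed events may therefore go unrecorded; it is not shown that they will.

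The size cannot be fixed from the documents. The capture figures are illustrations that rest on assumed rates and on independence between participants. The occlusion endpoint is unaffected, and 20 participants cannot establish delayed safety however well they are followed. The conclusion concerns the protocol text and would soften if the consent form already tells participants to report later symptoms to the study.

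**What to change.** - **Section 10.1, Participant Post-study Assessment.** Correct the advice sentence so that it addresses the participant. Add that the participant should notify the research team, as well as their own clinician, if a listed symptom occurs.
- **Same section.** Add one scheduled phone or e-mail contact at an interval set by the investigators. It should repeat the three questions and ask about bruising, any medical visit, and which leg is affected. Each leg receives a different device, so without the leg a symptom cannot be attributed to SMART TQ or CAT.
- **Section 16.1.** Name these two routes as the means of identifying later events, say who is meant by medical professionals, and reconcile the statement that related events are observed and addressed immediately with the post-discharge symptoms listed in section 10.1.

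The cost is about 21 short contacts by existing staff (20 study participants plus one in training), contact details kept until the contact is made, and an amendment to the protocol and consent form.

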17.0 Equipment/non-FDA Regulated Devices

17.1 Does the study involve the use of any unique non-medical devices/equipment?

Yes No

Please describe:

We are listing all the requirements by the FDA for the abbreviated IDE and addressing each requirement specifically. Please see each requirement for details. We do not have any FDA correspondence regarding this device at this point.

1. Labels the device in accordance with 812.5;

The novel layperson tourniquet, SMART TQ, will be labeled with the name and place of business of the manufacturer, the quantity of contents, and the statement: "CAUTION--Investigational device. Limited by Federal (or United States) law to investigational use."

2. Obtains IRB approval of the investigation after presenting the reviewing IRB with a brief explanation of why the device is not a significant risk device, and maintains such approval;

Why this device is not a significant risk device: This device is not a significant risk device because this device is not invasive, does not present serious risk to individuals' health, safety, and welfare.

The research team is seeking IRB approval and will maintain all communications and determinations from IRB.

3. Ensures that each investigator participating in an investigation of the device obtains from each subject under the investigator's care, informed consent under part 50 and documents it, unless documentation is waived by an IRB under 56.109(c).

All study participants will be asked to sign informed consent documents and they will keep one copy for their records. The research team will keep the other copy. All informed consent documents will be stored securely in a locked office.

4. Complies with the requirements of 812.46 with respect to monitoring investigations;

The study PI and study team will closely monitor the study procedures, data collection, and records throughout the entire investigation period.

5. Maintains the records required under 812.140(b) (4) and (5) and makes the reports required under 812.150(b) (1) through (3) and (5) through (10);

We will obtain all necessary regulatory approvals and maintain all relevant records. We understand that the level of pain may be experienced differently by different people, and therefore, some participants may express higher levels of pain than we anticipated. In this case, the tourniquet will be removed immediately and medical professionals are available to address any concerns.

6. Ensures that participating investigators maintain the records required by 812.140(a)(3)(i) and make the reports required under 812.150(a) (1), (2), (5), and (7);

We will maintain all study-related documents and make reports if necessary.

7. Complies with the prohibitions in 812.7 against promotion and other practices.

The device is for investigational use only and it will not be used for promotion or any other practices.

18.0

FDA-Regulated Products

18.1 Will any drugs, dietary supplements, biologics, or devices be utilized in this study?

- Drugs
- Dietary Supplements
- Biologics
- Devices
- N/A

18.3 Device Details:

- Are device(s) in this research being used in accordance to the approved labeling?
- Are device(s) in this research being used in a manner other than its approved labeling?

When adding a device indicate in the details section of the device if the use is either used in accordance to the approved labeling or in a manner other than it's approved labeling

View Details	Device Name	
No devices have been added to this Protocol		

18.4 Reporting Requirements for FDA-regulated research under IND and IDE:

Describe the process for complying with FDA regulatory requirements for adverse event reporting and adverse device effects reporting to the sponsor

18.5 Sponsor (organization/institution/company):

N/A

If applicable, provide sponsor contact information:

Defense Health Agency, Uniformed Services University of the Health Sciences, TTW program

